16.0 Health Information and Privacy Compliance

16.1 Select which of the following is applicable to your research:

My research does not require access to individual health information and therefore assert HIPAA does not apply.

I am requesting that all research participants sign a HIPCO approved HIPAA Disclosure Authorization to participate in the research (either the standalone form or the combined consent and HIPAA Authorization).

I am requesting the IRB to approve a Waiver or an alteration of research participant authorization to participate in the research.

Appropriate Use for Research:

An external IRB (e.g. Advarra) is reviewing and we are requesting use of the authorization language embedded in the template consent form in lieu of the U of M stand-alone HIPAA Authorization. Note: External IRB must be serving as the privacy board for this option.

16.2 Identify the source of Private Health Information you will be using for your research (Check all that apply)

MEDICAL PROTOCOL (HRP-590)

PROTOCOL TITLE: Piloting a Family-Based Intervention of Time-Restricted Eating to Treat Obesity

VERSION DATE: 07Sep2022

I will use the Informatics Consulting Services (ICS) available through CTSI (also referred to as the University's Information Exchange (IE) or data shelter) to pull records for me

I will collect information directly from research participants.

I will use University services to access and retrieve records from the Bone Marrow Transplant (BMPT) database, also known as the HSCT (Hematopoietic Stem Cell Transplant) database.

I will pull records directly from EPIC.

I will retrieve record directly from axiUm / MiPACS

I will receive data from the Center for Medicare/Medicaid Services

I will receive a limited data set from another institution

Other. Describe:

16.3 Explain how you will ensure that only records of patients who have agreed to have their information used for research will be reviewed.

16.4 Approximate number of records required for review:

We will ask that individuals who might meet study criteria, and who have not opted out of being contacted about research opportunities, be pulled into the data shelter. We will work with FV and the IE to have recruitment letters sent to potential participants. The MHealth system currently has ~ 14,000 children who are diagnosed with obesity who may be eligible for study participation.

16.5 Please describe how you will communicate with research participants during the course of this research. Check all applicable boxes

This research involves record review only. There will be no communication with research participants.

Communication with research participants will take place in the course of treatment, through MyChart, or other similar forms of communication used with patients receiving treatment.

Communication with research participants will take place outside of treatment settings. If this box is selected, please describe the type of communication and how it will be received by participants.

MEDICAL PROTOCOL (HRP-590)

PROTOCOL TITLE: Piloting a Family-Based Intervention of Time-Restricted Eating to Treat Obesity

VERSION DATE: 07Sep2022

16.6 Explain how the research team has legitimate access to patients/potential participants:

Individuals who would be pulled for a recruitment letter would be patients within the MHealth FV system who have not opted out of being informed about research studies.

16.7 Location(s) of storage, sharing and analysis of research data, including any links to research data (check all that apply).

In the data shelter of the [Information Exchange \(IE\)](#)

Store Analyze Share

In the Bone Marrow Transplant (BMT) database, also known as the HSCT (Hematopoietic Stem Cell Transplant) Database

Store Analyze Share

In REDCap (recap.ahc.umn.edu)

Store Analyze Share

In Qualtrics (qualtrics.umn.edu)

Store Analyze Share

In OnCore (oncore.umn.edu)

Store Analyze Share

In the University's Box Secure Storage (box.umn.edu)

Store Analyze Share

In an AHC-IS supported server. Provide folder path, location of server and IT Support Contact:

Store Analyze Share

In an AHC-IS supported desktop or laptop.

Provide UMN device numbers of all devices:

Store Analyze Share

Other. Describe:

MEDICAL PROTOCOL (HRP-590)

PROTOCOL TITLE: Piloting a Family-Based Intervention of Time-Restricted Eating to Treat Obesity

VERSION DATE: 07Sep2022

Indicate if data will be collected, downloaded, accessed, shared or stored using a server, desktop, laptop, external drive or mobile device (including a tablet computer such as an iPad or a smartform (iPhone or Android devices) that you have not already identified in the preceding questions

- I will use a server not previously listed to collect/download research data
- I will use a desktop or laptop not previously listed
- I will use an external hard drive or USB drive ("flash" or "thumb" drives) not previously listed
- I will use a mobile device such as a tablet or smartphone not previously listed

16.8 Consultants. Vendors. Third Parties. Individuals participating in the study will download apps for the Bluetooth scale and the Bluetooth toothbrushes that will track their weights and toothbrushing times. The app for the scale will allow the user to share their data and participants will be asked to email the study team with their results (this can be sent in a csv format to the study team). The app for the toothbrush does not allow for sharing so individuals can screenshot their data and send to the study team or simply show the study team their phone to review the data at their visits. Data that is transmitted to the study team from the participant (such as the csv file for the scale data) will be stored in Box. It is our understanding from meeting with the HIPCO office that participants are free to send data to us and only after it is received by us, does it need to be protected.

16.9 Links to identifiable data: Csv files that the participants send to us that contain their Bluetooth scale information will be stored in Box as it is HIPAA compliant.

16.10 Sharing of Data with Research Team Members. Data will be kept in REDCap and Box and only those individuals who are working on the study will have access to these items.

16.11 Storage of Documents: Paper documents will be kept in individual participant binders and will be kept in an office that is locked when not in use. Electronic records may be kept in Box and REDCap, which utilize two level authentication.

16.12 Disposal of Documents: We anticipate keeping data for at least six years. When data is ready to be destroyed, a company that specializes in the shredding of confidential documents will be utilized to destroy any paper files.

17.0 Confidentiality

17.1 Data Security: Absolute confidentiality will be maintained. All data will be stored in locked offices and will not be released without consent of the participant. Data that is collected will be entered into REDCap which is only accessible by the study

MEDICAL PROTOCOL (HRP-590)

PROTOCOL TITLE: Piloting a Family-Based Intervention of Time-Restricted Eating to Treat Obesity

VERSION DATE: 07Sep2022

team. Data to be used in scientific presentations or publications will not contain participant identifiers.

18.0 Provisions to Monitor the Data to Ensure the Safety of Participants

18.1 Data Integrity Monitoring. The biostatisticians will issue queries on data that is analyzed where data is missing or does not seem to be correct and the study team will review the study file and make corrections.

18.2 Data Safety Monitoring. Case report forms will be reviewed for accurate completion by individuals within the Center for Pediatric Obesity Medicine.

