8.2 Exclusion Criteria

- Concurrent participation in another weight loss study
- Taking any medications for weight loss
- Pregnancy or anticipation of pregnancy in next 6 months (for the parent)
- 3+ on Eating Disorder Survey (see attached)
- Must be on a stable dose of any weight-altering medications

8.3 Prescreening/Consent: Individuals who appear to meet the study criteria based on a pre-screening telephone call will be asked to participate in a virtual (video) visit. At that visit, consent will be discussed and obtained, height and weight will be self-reported by parent for both parent and child, so that estimated BMI can be calculated, and inclusion/exclusion criteria will be reviewed. Individuals who meet the BMI requirement and the inclusion/exclusion criteria will enroll in the study.

Following consent and prior to the Baseline/Week 0 session, parents will be

MEDICAL PROTOCOL (HRP-590)

PROTOCOL TITLE: Piloting a Family-Based Intervention of Time-Restricted Eating to Treat Obesity

VERSION DATE: 07Sep2022

contacted by the University of Minnesota Nutrition Coordinating Center (NCC) staff and will be asked to provide three 24-hour dietary recalls for themselves and for their child (for a total of six). NCC staff will be blinded to participant intervention assignment. Using this 24-hour dietary recall data, we will calculate the daily average caloric intake and healthy eating index, as well as the eating window.

Baseline/Week 0: Individuals will be asked to come to the Delaware Clinical Research Unit (DCRU). At that visit, height and weight will be measured so that BMI can be calculated. Individuals who no longer meet inclusion/exclusion criteria will be excluded (e.g., outside BMI range based on in-person measurement compared to self-reported). Participants who meet the inclusion/exclusion criteria will be randomized to their intervention group. Participants will be provided with a Bluetooth-enabled scale and instructed to weigh themselves once per week. Participants will also be provided with Bluetooth-enabled toothbrushes. Participants randomized to the TRE treatment will be asked to brush their teeth twice daily and to brush their teeth within 30 minutes after the evening meal to note that they have ceased eating until the next day.

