Participants randomized to SOC will have a dietary session with a dietitian to discuss food portions and food selections that encourage reduced caloric intake. They will be given portioned dishes as part of this treatment. Participants randomized to TRE will meet with the dietitian to discuss the length and timing of the eating window. All parents will be asked to complete demographic information and questionnaires. Parents will be told that they will receive periodic emails (see schedule of events) asking them to log into REDCap and complete a survey about what time the family started and stopped eating meals for the day.

Weeks 1, Week 2, Week 3, Week 4, Week 6, Week 8, Week 10: Parents will have a dietary session with the dietitian to discuss their respective intervention. That is, parents in TRE will discuss implementation of the eating window and parents in SOC will discuss food portions and food selections that encourage reduced caloric intake. Parents will be reminded that they should utilize the Bluetooth-enabled scale to weigh themselves as well as their child once per week. Parents will be reminded to fill out the REDCap survey daily and will be reminded to utilize the Bluetooth-toothbrush.

Week 12: Participants will return to the Delaware Clinical Research Unit. They will receive a session with the study dietitian. The height and weight of the parent and the child will be measured and BMI calculated. The parent will be asked to fill out questionnaires about eating as well as a satisfaction survey.

MEDICAL PROTOCOL (HRP-590)

PROTOCOL TITLE: Piloting a Family-Based Intervention of Time-Restricted Eating to Treat Obesity

VERSION DATE: 07Sep2022

Parents will be contacted by a Registered Dietician from the University of Minnesota Nutrition Coordinating Center (NCC) staff and will be asked to provide three 24-hour dietary recalls for themselves and for their child (for a total of six).

Follow-up: The parent will receive a satisfaction survey to be completed electronically at 1, 3, and 6 months following treatment .

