13.0 Risks to Participants

13.1 Foreseeable Risks: Risks for this study are minimal and include discomfort with recalling and reviewing meals, tiring of filling out daily REDCap inquiries, and potential frustrations (for the TRE group) with trying to brush their teeth in the evening within 30 minutes of finishing their evening meal. There could be discomfort or dissatisfaction with limiting food intake to the eating window hours and/or with limiting caloric intake per standard of care recommendations. There is also a risk of breach of confidentiality.

13.2 Reproduction Risks: Not applicable.

13.3 Risks to Others: Not applicable.

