20.0 Compensation for Research-Related Injury

20.1 Compensation for Research-Related Injury:

Treatment for injuries that result from participating in the research activity will be available. Those treatments include first aid, emergency treatment and follow-up care as needed. Care for injuries will be billed in the ordinary manner, to the subject or their insurance company. Subjects will be encouraged to contact the study team if they think that they have suffered a research related injury.

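### Safety monitoring is described only as form review, and no step systematically collects, reviews or summarises unwanted effects in a trial that restricts eating in children aged 3-9

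*Combined protocol and SAP*

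**What the plan says.** Section 18 is headed as the provision for participant safety and has two parts. On data integrity (18.1): "The biostatisticians will issue queries on data that is analyzed where data is missing or does not seem to be correct". On data safety (18.2): "Case report forms will be reviewed for accurate completion by individuals within the Center for Pediatric Obesity Medicine". Neither part defines an adverse event, gives a review frequency or a reporting route, or assigns anyone to look at safety information.

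The visit descriptions in Section 8.3 cover three kinds of contact after baseline:
- Virtual sessions: "Parents will have a dietary session with the dietitian to discuss their respective intervention", followed by reminders about the scale, the survey and the toothbrush.
- Week 12: height and weight, a dietitian session, dietary recalls, and "The parent will be asked to fill out questionnaires about eating as well as a satisfaction survey".
- After treatment: "The parent will receive a satisfaction survey to be completed electronically at 1, 3, and 6 months following treatment".

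The Schedule of Events has no harms row in any column. Section 3 names no safety outcome and Section 15 no harms analysis.

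The protocol does recognise possible unwanted effects. Section 13.1 states that "There could be discomfort or dissatisfaction with limiting food intake to the eating window hours", and says the same of calorie limits in the control arm. Section 20.1 says: "Subjects will be encouraged to contact the study team if they think that they have suffered a research related injury".

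**The concern.** Both arms restrict eating in children aged 3-9: one by a 10-12 hour window, the other by instruction based on a 1200-1500 calorie diet. Under Section 4.1 the child attends only baseline and week 12, and parents alone attend the virtual sessions. Between those two visits staff need not see the child, so asking the parent is the practical way to learn of a problem, and no such question is described.

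The pilot is meant to inform a fully powered trial. It could report good acceptability in young families without having asked systematically about unwanted effects. The next protocol would then have no harm rates, even rough ones, for either arm.

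**Working it through.** The plan gives no harms figure to reproduce. Its only power statement (Section 15) concerns BMI change and has no bearing here. The check is therefore a reading of each place where harms could enter, followed by two small calculations.

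**1. Where harms could enter**
- Endpoints (Section 3): recruitment, adherence, burden, weight/BMI. No safety outcome.
- Schedule of Events (Section 5.1): no harms row from consent to month 6.
- Visit descriptions (Section 8.3): no harms question at any contact.
- Withdrawal (Section 12): participant choice only.
- Analysis (Section 15): diet, eating and feeding behaviour, appetite and quality of life are compared as outcomes. No harms summary.
- Monitoring (Section 18): data queries and form review.
- Injury (Section 20.1): a passive route that depends on the family judging that an injury is research-related.

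**2. Contacts already available**

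The schedule shows baseline, virtual sessions at weeks 1, 2, 3, 4, 6, 8 and 10, and week 12: 1 + 7 + 1 = 9. The payment total in Section 11.3 confirms the count: 2 × $35 + 7 × $15 = $70 + $105 = $175, as stated. Eight of the nine contacts fall after the intervention starts.

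**3. What systematic asking would yield**

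Inputs: 10 children per arm (Section 10.1) and 70-80% retention (Section 3.1), so 7-8 children per arm. With zero events in n children, the one-sided 95% upper limit is 1 − 0.05^(1/n):
- n = 10: 25.9%
- n = 8: 31.2%
- n = 7: 34.8%
- n = 20 (both arms pooled): 13.9%

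The chance of seeing at least one case of an effect with a true frequency of 5% (an illustrative value, not from the documents) is 1 − 0.95^n: 40.1% for n = 10 and 64.2% for n = 20.

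These limits apply only if every family is asked. With spontaneous reporting alone the number of families effectively asked is unknown, so zero reports supports no upper limit.

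**The case against.** The best defence has five parts.

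- **A route exists.** A reader might infer from Section 18 that a problem could never reach the record. Section 20.1 contradicts that. The route is passive and has no form or time window, but it is there.
- **Relevant data exist.** A reader might infer that the trial ends with no harm data at all. That goes too far. Weekly weights, week-12 height and weight, repeat dietary recalls, eating-behaviour questionnaires, Peds-QL and satisfaction surveys could all show adverse change in either arm. The satisfaction survey may even touch the discomfort foreseen in Section 13.1; its items are not in the documents. What stands is that none of these is designated or reviewed for safety, and none is described as recording a specific event.
- **The forms are not available.** The case report forms might contain an adverse-event field. One cannot claim that no contact captures harms, only that the protocol describes no such capture, review or summary.
- **Risk is rated minimal.** Section 13.1 says so, and intake within the eating window is ad libitum. This justifies light monitoring, and nothing heavier is asked for here. Nor do the documents support saying that feasibility and acceptability cannot be concluded without harms data, because Section 3.1 defines them by recruitment, adherence and burden.
- **Session time is an outcome.** Sections 3.1 and 15 compare staff time between arms, so added questions could distort that comparison. This stands, and the fix must allow for it.

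It is also tempting to ask that the eating disorder screen be repeated. The criterion reads "3+ on Eating Disorder Survey (see attached" and the survey itself is not in the documents. They do not show who completes it or whether it suits repeat use, so that request is not made.

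**Conclusion.** The point holds as a gap in systematic harms ascertainment. As described, the plan has a safety provision limited to form review, no scheduled inquiry, no reviewing role and no summary by arm. Harms could not be reported systematically or compared between arms, and silence could not be read as safety. The change should be made, but it does not threaten the pilot's stated feasibility measures.

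The precision regained is limited: an upper limit of about 26% per arm with all 10 children and no events, or about 31-35% with 7-8. The conclusion rests on the protocol text alone and assumes that no unseen form supplies a systematic harms question. Even if one did, the review role and the by-arm summary would still be absent from the text.

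**What to change.** - Add one standard question on unwanted effects, answered by the parent for themselves and on behalf of the child, at the 7 virtual sessions and week 12, worded identically in both arms.
- Record the answers on the case report form and add a row to the Schedule of Events.
- Name in Section 18.2 the role that reviews these reports.
- Add to Section 15 a descriptive summary by arm, separately for parents and children, without hypothesis tests.
- Log the time spent on this question separately and exclude it from total intervention time. Otherwise it would lengthen a compared outcome, possibly by different amounts in the two arms if events differ.

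The cost is a few minutes per session, one form page and one descriptive table. No extra visits are needed, and neither intervention changes.

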19.0 Provisions to Protect the Privacy Interests of Participants

19.1 Protecting Privacy: see HIPCO ancillary review.

19.2 Access to Participants: Please refer to the recruitment section.

20.0 Compensation for Research-Related Injury

20.1 Compensation for Research-Related Injury:

Treatment for injuries that result from participating in the research activity will be available. Those treatments include first aid, emergency treatment and follow-up care as needed. Care for injuries will be billed in the ordinary manner, to the subject or their insurance company. Subjects will be encouraged to contact the study team if they think that they have suffered a research related injury.

21.0 Consent Process

21.1 Consent Process (when consent will be obtained):

Consent will be obtained by the study team after explaining the entire study in detail, asking the participants to explain the purpose, risk and benefits, and other details of the study, and giving the participants an opportunity to ask questions. A copy of the signed consent form will be given to the participants.

21.2 Waiver or Alteration of Consent Process (when consent will not be obtained): Not applicable.

21.3 Waiver of Written/Signed Documentation of Consent (when written/signed consent will not be obtained): Not applicable

21.4 Non-English Speaking Participants: Not applicable.

21.5 Participants Who Are Not Yet Adults (infants, children, teenagers under 18 years of age): Children aged 3-9 will be allowed to enroll in this study. For children aged 3-7, the parent will sign a parental consent form to indicate that the child may enroll in the study and no assent will be collected. Participants who are aged 8-9 will be asked to sign an assent form and their parent will be asked to sign a parental consent form. We are planning on having only one parent signature in the parental consent form.

MEDICAL PROTOCOL (HRP-590)

PROTOCOL TITLE: Piloting a Family-Based Intervention of Time-Restricted Eating to Treat Obesity

VERSION DATE: 07Sep2022

21.6 Cognitively Impaired Adults, or adults with fluctuating or diminished capacity to consent: Not applicable.

21.7 Adults Unable to Consent: Not applicable.

21.8 Assent: Assent will be utilized for participants who are aged 8-9. No assent will be utilized for participants aged 3-7.

22.0 Setting

22.1 Research Sites:

- Delaware Clinical Research Unit
- University of Minnesota Nutrition Coordinating Center (NCC)

22.2 International Research: Not applicable.

23.0 Multi-Site Research: Not applicable.

24.0 Coordinating Center Research: Not applicable.

25.0 Resources Available: Not applicable.

